1.3 Schedule of activities

Table 1-2: Schedule of activities (initial fixed cycle)

Procedure	Gap Period ^a	Treatment Period								Observation Period				No treatment with rozanolixizumab		
		V1 (BL) ^{b,c}	V2	V3	V4	V5	V6	V7	V8 (PEOT)	V9	V10	V11	V12			
Visit	Scr ^a	V1 (BL) ^{b,c}	V2	V3	V4	V5	V6	V7	V8 (PEOT)	V9	V10	V11	V12	-	-	EOS
Visit type	S	S	H ^d	S	S	S	H ^d	S	S	S	VR	S	VR	S	S	S
Day (visit window) ^e	-28 to -1	1	3 (±1)	8 (±2)	15 (±2)	22 (±2)	29 (±2)	36 (±2)	43 (±2)	71 (±7)	99 (±7)	127 (±7)	155 (±7)	Every 4 weeks (±7)	Every 12 weeks (±7)	- (±2)
Written informed consent	X	X								X ^f						
Demographic and Baseline characteristics	X	X								X ^f						
Verification of inclusion/exclusion criteria	X ^g	X ^h								X ^f						
Medical history update		X								X ^f						
Prior and concomitant medications and medical procedures	X	X	X	X	X	X	X	X	X	X	X	X	X	X	X	X
Body weight	X	X														
Psychiatric history/C-SSRS	X															
Query for suicidality ⁱ		X		X	X	X	X	X	X		X		X	X	X	X
IGRA TB test ^j	X															X
TB Signs and Symptoms questionnaire	X	X							X				X		X	X
12-lead ECG	X	X		X												X
Full physical examination ^k	X	X														
Brief physical examination ^k				X	X	X		X	X	X		X		X	X	X

Procedure	Gap Period ^a	Treatment Period								Observation Period				No treatment with rozanolixizumab		
		V1 (BL) ^{b,c}	V2	V3	V4	V5	V6	V7	V8 (PEOT)	V9	V10	V11	V12			
Visit	Scr ^a	V1 (BL) ^{b,c}												-	-	EOS
Visit type	S	S	H ^d	S	S	S	H ^d	S	S	S	VR	S	VR	S	S	
Day (visit window) ^e	-28 to -1	1	3 (±1)	8 (±2)	15 (±2)	22 (±2)	29 (±2)	36 (±2)	43 (±2)	71 (±7)	99 (±7)	127 (±7)	155 (±7)	Every 4 weeks (±7)	Every 12 weeks (±7)	- (±2)
Vital signs ^l	X	X	X	X	X	X	X	X	X	X	X	X	X	X	X	
Call or enter IRT to register the visit	X	X		X	X	X	X	X	X ^m						X ⁿ	
Study participants identification card assigned		X														
Recording of AEs	X	X	X	X	X	X	X	X	X	X	X	X	X	X	X	
Pregnancy test (serum)	X															
Pregnancy test (urine) ^o		X													X	
PTT and INR	X															
Hematology, serum chemistry	X	X		X		X		X		X		X		X	X	
Serology (HIV, Hepatitis B, and Hepatitis C)	X															
Urinalysis	X	X			X			X		X		X		X		
Blood sampling for PK ^p		X	X ^q			X			X		X				X	
Blood sampling for ADA		X			X			X		X		X			X	
Blood sampling for total IgG and IgG subclasses	X	X	X	X	X	X	X ^q	X	X	X					X	
Blood sampling for exploratory safety biomarker analysis															X ^r	

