The dose may be adjusted to 7mg/kg or 10mg/kg at the beginning of each treatment cycle based on the Investigator's discretion. Rules for dose modification and temporary treatment hold are described in Section [6.6](#) and Section [6.7](#). The minimal time to start the next treatment cycle is 4 weeks following the last dose of the treatment period of the previous cycle. If a study participant requires treatment earlier than 4 weeks, IgG levels from the previous cycle should be considered and discussed with the Medical Monitor. A new treatment cycle **should not** be initiated until total IgG level is ≥ 2 g/L.

Participants in MG0007 will remain on their gMG background medications ([Table 6-3](#)). With the exception of corticosteroids and AChE inhibitors, all gMG medication doses should be maintained during each respective 6-week treatment cycle and efforts should be made to maintain a stable dose during the first 8 weeks of the Observation Period.

Study participants who receive rescue therapy (IVIg, PEX, SC Ig, or iv corticosteroid) during the Treatment Period are not eligible to receive any further treatment with rozanolixizumab, must complete an additional 8 weeks of follow up after the last dose of rozanolixizumab. Study participants must complete the first 8 weeks of the Observation Period after the last dose of rozanolixizumab prior to completing the EOS visit assessments, and subsequently will be withdrawn from the study (Section [4.4](#)).

Those patients who received rescue therapy (IVIg, PEX, SC Ig, or iv corticosteroid) during the observation or no treatment with rozanolixizumab periods may continue in the study at the Investigator's discretion and after discussion with Medical Monitor and/or UCB Study Physician. The following cycle of rozanolixizumab should in general not start earlier than 4 weeks following the last dose of IVIg, SC Ig, or iv corticosteroids or the last PEX session, unless there is a medical reason, and an earlier treatment initiation is being considered [REDACTED] for the study participant as agreed upon with the Medical Monitor and/or UCB Study physician.

Study participants (not withdrawn from the study; criteria outlined in Section [7.2](#)) will continue in the study and until product approval or until transition to a managed access program (MAP), if

available, as indicated per the Sponsor, and according to local guidance. For country-specific requirements, see Appendix 8 (Section 10.8).

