9.4.2.2 Pharmacodynamic analyses

For all other endpoints relating to PD endpoints, descriptive statistics for the value, change from Baseline, and percentage change from Baseline will be tabulated by dose arm, and time point for the SS for each cycle. The PD endpoints will include serum total IgG, IgG subclass levels, and anti-MuSK and -AChR autoantibodies.

For the analysis of the IgG data, in case rescue therapies are taken, only the data up to the start date of rescue therapy will be utilized for the summary tables. Listings will contain all IgG data and the measurements of study participants, which have been excluded from the summary tables. In cases where a study participant drops out, no missing value imputation will be performed for the IgG. Absolute and relative IgG reduction for a cycle will be calculated with the cycle Baseline value as reference. As for safety, the IgG reduction analyses will be compared between cycles.

Population PD or population PK/PD analyses may be conducted for the PD variables of interest. Details of such PD or PK/PD analyses will be described in a separate DAP. The results of the analyses will not be reported in the CSR but in a separate report.

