2.2.3.2 Pharmacodynamic endpoints

For each 6-week treatment cycle and Observation Period (where applicable):

- Minimum value and maximum decrease from Baseline (Day 1) in total serum IgG and IgG subclasses concentration over time
- Change from Baseline (Day 1) in serum IgG subclasses concentration over time
- Change (absolute and percentage) from Baseline (Day 1) in MG-specific autoantibodies at each scheduled assessment during the Treatment and Observation Periods

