10.2 Pharmacodynamics

10.2.1 Total serum IgG and IgG subclasses

Total serum IgG concentrations and IgG subclasses will be summarized by study cycle, actual dose level received within study cycle, overall, and time point for observed values, change from Baseline, and percentage change from Baseline for each cycle. For the analysis of the IgG data, in case rescue therapies are taken, the data up to (not including) the start date of rescue therapy and the data 8 weeks after the start date of rescue therapy will be utilized for the summary tables, ie the data from (including) start date of rescue therapy, to 8 weeks after start date of rescue therapy will be excluded from summary analysis. In cases where a study participant drops out, no missing value imputation will be performed for the IgG.

The maximum change from Baseline in total serum IgG (absolute and percentage change) will be reported in the listing and summarized by study cycle, actual dose level received within study cycle, and RLZ total. If there is no decrease from Baseline in total serum IgG in a given study participant, the maximum change will be reported as the smallest increase from Baseline.

Additionally, summary of total IgG by fixed dose and weight subgroups will be conducted as specified in [Section 4.9.2](#).

Median and median percentage change from Baseline values in total serum IgG will be plotted over time by study cycle, actual dose level received within study cycle, and RLZ total with Baseline bodyweight groups (<50kg, 50kg-<70 kg, 70kg-<100kg, \geq 100kg) overlaid on the same plot.

Spaghetti plots will be provided for absolute IgG and percentage change from baseline in IgG over time stratified by treatment group and Baseline bodyweight group (<50kg, 50kg-<70 kg, 70kg-<100kg, \geq 100kg) where the Baseline bodyweight group is multipaneled or overlaying with different colors within each treatment group for each cycle.

A boxplot of maximum percentage from Baseline in total IgG up to Day 43 will be generated by study cycle and administered dose as specified in [Section 4.9.2](#).

A subject plot for MG-ADL, QMG, and IgG over time for participants with weight below 50kg will also be provided.

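### SAP 10.2.1 specifies no analysis for the participant minimum IgG or for any subclass extreme, and its by-cycle maximum change rests on about seven samples on the initial-cycle schedule but two on the later one

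*SAP*

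**What the plan says.** The pharmacodynamic endpoint reads the same in Protocol Section 3 and SAP 2.2.3.2, for each treatment cycle and its Observation Period where applicable: "Minimum value and maximum decrease from Baseline (Day 1) in total serum IgG and IgG subclasses concentration over time". Subclass change over time is listed separately, as an endpoint of its own.

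For IgG extremes and related displays the SAP specifies:

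- By-visit tables (SAP 10.2.1): "Total serum IgG concentrations and IgG subclasses will be summarized by study cycle", further split by dose and time point, as observed value, change and percentage change.
- Extreme value (SAP 10.2.1): "The maximum change from Baseline in total serum IgG (absolute and percentage change) will be reported in the listing and summarized by study cycle". This is for total IgG only, and no time window is stated.
- Figure (SAP 10.2.1): "A boxplot of maximum percentage from Baseline in total IgG up to Day 43 will be generated by study cycle and administered dose".
- ADA table (SAP 10.3.2): mean maximum percentage change in total IgG to Day 43, by ADA category and cycle.

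Protocol 9.4.2.2 sets the reference value, "Absolute and relative IgG reduction for a cycle will be calculated with the cycle Baseline value as reference", and adds: "As for safety, the IgG reduction analyses will be compared between cycles". It gives no method for that comparison. The SAP specifies no between-cycle contrast, and SAP 4.6 states that all analyses are descriptive.

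The row "Blood sampling for total IgG and IgG subclasses" appears in both Protocol Table 1-2 (initial cycle) and Table 1-3 (subsequent cycles), but with different visits marked.

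**The concern.** There are two separate problems.

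First, a listed endpoint is only partly analysed. A programmer who follows SAP 10.2.1 will produce no participant-level minimum for total IgG and no extreme-value result for any subclass. The report would then state an endpoint for which it has no result.

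Second, an extreme taken over more samples tends to be more extreme. The protocol says IgG reduction will be compared between cycles, and the SAP shows maximum change by cycle. If the initial cycle has more chances to catch a low value, part of any difference between cycles comes from the sampling schedule and not from the drug.

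**Working it through.** The documents give no figure for IgG change by cycle, so there is nothing of the plan's own to reproduce. The check compares the texts and then sizes the sampling effect.

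**Step 1. Endpoint against analysis.**

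| Endpoint component (SAP 2.2.3.2) | Extreme-value analysis in SAP 10.2.1 |
|---|---|
| Total IgG, minimum | none |
| Total IgG, maximum decrease | listing, summary, boxplot |
| Each subclass, minimum | none |
| Each subclass, maximum decrease | none |

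Three of the four components have no analysis. SAP 3.9 does list another IgG change (handling of values after rescue therapy) but not this one.

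**Step 2. Samples to Day 43.**

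- Table 1-2: V2 to V8, that is Days 3, 8, 15, 22, 29, 36 and 43, so 7 post-baseline samples.
- Table 1-3: V4 and V7, that is Days 22 and 43, so 2.

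The Table 1-2 row is one cell short in the text available, so its alignment is inferred. Appendix 11 confirms a screening IgG sample, and with that as the first mark the home-collection footnote falls on V6, which is a home visit.

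**Step 3. Direction.** The set {3, 8, 15, 22, 29, 36, 43} contains {22, 43}. A maximum decrease over the larger set can never be smaller than over the subset. To Day 43, then, the initial schedule reads equal or deeper for the same curve. The argument is strict only to Day 43. After that the schedules no longer nest (Day 71 against Day 99, then EOS in each).

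**Step 4. Size, under assumptions.** The documents give no within-person variability. I assumed a true fraction remaining on day d of 1 − p(1 − exp(−(d − 1)/τ)), with p = 0.6 or 0.7 and τ = 5, 8 or 12 days. Post-baseline values carry independent lognormal error with CV 5, 10 or 15%, and the baseline is error-free. Each of the 18 settings had 200,000 simulated participants. A rapid fall followed by a plateau matches what Protocol 4.3 expects.

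| Plateau p | τ (days) | CV | Mean maximum change, 7 samples | 2 samples | Gap (points) |
|---|---|---|---|---|---|
| 0.7 | 12 | 5% | −68.2% | −67.8% | 0.33 (smallest) |
| 0.7 | 8 | 10% | −71.5% | −69.9% | 1.64 |
| 0.6 | 5 | 10% | −63.7% | −61.7% | 2.04 |
| 0.6 | 8 | 15% | −64.3% | −61.2% | 3.10 (largest) |

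Gaps are taken before rounding the means. The lowest of the seven values fell outside Days 22 and 43 in 25–57% of simulated participants.

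**Step 5. Who is in Cycle 1.** Under Protocol 4.1.1, MG0004 entrants go straight to the Observation Period of the initial cycle. Footnote b of Table 1-2 sends them to the subsequent-cycle table. SAP 8.1 counts cycles whether or not the first was mandatory. MG0004 entrants therefore appear to have their first treated cycle on the two-sample schedule, so Cycle 1 may mix both.

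**Step 6. Sensitivity to the cycle baseline.** Percentage change = 100 × (nadir/baseline − 1). Hold the nadir at 3.3 g/L, the MG0002 mean in Protocol 4.3, and vary an assumed baseline:

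- 10 g/L gives −67.0%
- 8 g/L gives −58.8%
- 6 g/L gives −45.0%

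The measure is sensitive to the baseline. The documents do not give the baselines of any cycle, so this shows leverage and is not a prediction.

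**The case against.** The best defence is that the plan already holds most of what is needed.

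- **By-visit tables.** Observed g/L at Days 22 and 43 is summarised per cycle, for total IgG and subclasses. That view depends on neither the cycle baseline nor the number of samples. This stands, and it allows a partial matched-day comparison. It does not replace the endpoint, because participants reach their lowest value at different visits.
- **Recoverable minimum.** For total IgG, a participant's minimum equals cycle baseline plus maximum absolute change. This is right for the listing, and for the mean if the same participants contribute. The median, SD and range cannot be recovered from the summaries, and nothing comparable exists for the subclasses.
- **Low-IgG count.** SAP 13.6 flags IgG at or below 1 g/L. A count at one threshold is not a distribution of minima.
- **Purpose of the displays.** The boxplot serves the fixed-dose question in SAP 4.9.2, and the ADA table contrasts ADA categories. Neither is built as a contrast of cycles. This stands, but both are shown by cycle, and the protocol announces a comparison between cycles.
- **Cycle-baseline reference.** This is the protocol's own choice, so using it is not an SAP error.

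A reader might also infer that later cycles will show a falsely smaller reduction because their baselines are still suppressed: "The minimal time to start the next treatment cycle is 4 weeks following the last dose", with total IgG of at least 2 g/L. The documents do not support that direction. Cycle 1 baselines can be suppressed too. For direct MG0003 entrants the baseline is that study's EOS visit, after an 8-week Observation Period, and MG0004 entrants come from weekly dosing. Later cycles start on symptom worsening, and SAP 9.11 provides for intervals up to 1000 days, so a later baseline may be the more recovered one.

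**Conclusion.** The omission is established from the text alone: SAP 10.2.1 gives no participant minimum for total IgG and no minimum or maximum decrease for any subclass, and SAP 3.9 does not record it.

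The by-cycle maximum change to Day 43 is not like-for-like between the two schedules. Its direction follows from the visit sets as read in Step 2. Its size, about 0.3 to 3 percentage points, rests on the assumed curves and within-person CVs of 5–15%. That Cycle 1 mixes the two schedules is likely from the text but not stated outright.

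The documents do not support a claim that the between-cycle comparison is biased by tens of points, or that it would falsely show waning. The baseline part cannot be sized or signed, and the sampling part alone is small. IgG falls under the study's other objectives and no test is planned, so no formal inference is at stake. The point is worth correcting for completeness and for a fair reading across cycles.

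**What to change.** In SAP 10.2.1:

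1. Derive and summarise, per cycle, each participant's minimum value and maximum decrease for total IgG and for each subclass, as the endpoint states, with the time window given. If any part is to be dropped, record and justify it in SAP 3.9.
2. For any display used to compare cycles, add a version of the minimum and maximum restricted to Days 22 and 43. Keep the all-sample nadir as a within-initial-cycle result.
3. Show cycle-baseline IgG beside the change measures, so that a reader can see whether a different percentage reflects a different starting point.

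Percentage change from the pre-rozanolixizumab baseline is optional. The rule in SAP 10.3.1 for the ADA baseline would identify it, but for many participants it needs lead-in data.

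The cost is SAP wording and a few table columns from data already collected. The common-day reduction in the initial cycle will look slightly smaller than the all-sample one.

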10.2.2 MG-specific autoantibodies

Participants with <0.05 nmol/L in the MuSK assay at Baseline visit will be assigned to MuSK Negative.

MG-specific autoantibodies [anti-MuSK/anti-AChR v1 (determined with reagent 1)/anti-AChR v2 (determined with reagent 2)] will be summarized by study cycle, actual dose level received within study cycle, and RLZ total, at scheduled visit for observed values and absolute changes from Baseline by the participants who are anti-MuSK or anti-AchR autoantibody-positive at the MG0003 Baseline visit. For anti-AChR, if both anti-AChR v1 and anti-AChR v2 exist in one cycle, only anti-AChR v2 will be used in the summary table.

Anti-MuSK will also be summarized by study cycle, actual dose level received within study cycle, and RLZ total, at scheduled visit for observed values and percentage changes from Baseline by the participants who are anti-MuSK autoantibody-positive at the MG0003 Baseline visit.

Anti-AChR (values determined either with reagent 1 or 2) will be summarized by study cycle, actual dose level received within study cycle, and RLZ total, at scheduled visit for percentage changes from Baseline by the participants who are anti-AchR autoantibody-positive at the MG0003 Baseline visit.

The maximum change from Baseline in MG-specific autoantibodies [absolute (anti-MuSK, anti-AChR v1, anti-AChR v2) and percentage change (anti-MuSK, anti-AChR v1&v2 combined)] will be reported in the listing and summarized for each treatment. If there is no decrease from Baseline in MG-specific autoantibodies in a given study participant, the maximum change will be reported as the smallest increase from Baseline.

Median absolute and median percentage change from Baseline values in MG-Specific autoantibodies will be plotted over time by study cycle, RLZ dose level received within study cycle, and RLZ total with all treatments overlaid on the same plot for positive participants at MG0003 Baseline. Additionally, median percentage change from Baseline in anti-MuSK and median percentage change from Baseline of total IgG, and MG-ADL, QMG, MG-C mean change from Baseline will be plotted by study cycle, actual dose level received within study cycle and RLZ total for positive participants at MG0003 Baseline. The same plot will be repeated for median percentage change from Baseline values in anti-AChR for positive participants at MG0003 Baseline.

MG-specific autoantibodies will be listed, together with total IgG, IgG subclasses for all participants, and MG-ADL, QMG, MG-C change from Baseline.

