2 INTRODUCTION

Rozanolixizumab is a humanized IgG4 monoclonal antibody that is being developed as an inhibitor of the activity of the FcRn for IgG.

By blocking the activity of FcRn, rozanolixizumab accelerates the catabolism of IgG antibodies, including IgG pathogenic autoantibodies. The aim is to reduce the concentration of pathogenic IgG in patients with autoimmune diseases mediated by the action of IgG autoantibodies.

The FcRn recycles IgG and albumin and transports it bidirectionally across epithelial barriers. Recent studies have shown that FcRn rescues both IgG and albumin from intracellular lysosomal degradation by recycling it from the sorting endosome to the cell surface ([Roopenian and Akilesh, 2007](#)). FcRn may also mediate transcytosis of IgG to facilitate its distribution within tissues. Rozanolixizumab has been specifically designed to block IgG binding to FcRn without blocking the binding and recycling of albumin.

Rozanolixizumab binds with high affinity to FcRn at both neutral and acidic pH. Immunoglobulin G that is constitutively taken up by pinocytosis into cells fails to bind to FcRn, even at the acidic pH found in the endosome. It is therefore not recycled and is trafficked to the lysosomes for degradation.

Production of pathogenic IgG autoantibodies is the major pathophysiology leading to a number of autoimmune diseases, which include MG, pemphigus vulgaris, [REDACTED], Goodpasture's syndrome, neuromyelitis optica, Guillain-Barré Syndrome, and chronic inflammatory demyelinating polyradiculoneuropathy.

As individual disease entities, IgG autoantibody-mediated conditions are relatively rare. Treatment of these disorders remains a difficult clinical problem, requiring in many of these conditions the long-term use of corticosteroids alone or combined with other immunomodulatory therapy. These therapeutic approaches are not effective in all patients and conditions and have broad immunosuppressive effects causing considerable toxicity and treatment-related morbidity.

Treatments aimed at reducing the quantity of circulating IgG autoantibodies, including plasmapheresis, immunoabsorption, or high dose IVIg, are being used for primary and secondary therapy of autoimmune diseases. The therapeutic approach of these treatments is thought in part to be based on lowering levels of pathogenic autoantibodies, which represents rational and effective treatment modalities of autoimmune diseases.

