6.5.4 Rescue medication

The study site will supply rescue therapy that will be obtained locally. Rescue therapy will be given as per standard of care and at the discretion of the Investigator. Study participants who continue to experience moderate to severe symptoms despite treatment with rozanolixizumab may be treated with the following as rescue therapy:

- IVIg
- SC Ig
- PEX, or plasmapheresis
- iv corticosteroids at a higher dose than previous oral dose

Participants who are treated with rescue therapy during the Treatment Period are not eligible to receive any further treatment with rozanolixizumab. Study participants must complete the first 8 weeks of the Observation Period after the last dose of rozanolixizumab prior to completing the EOS visit assessments, and subsequently will be withdrawn from the study (Section 4.4).

Those patients who received rescue therapy during the observation or no treatment with rozanolixizumab periods may continue in the study at the Investigator's discretion and after discussion with Medical Monitor and/or UCB Study Physician. The following cycle of rozanolixizumab should in general not start earlier than 4 weeks following the last dose of IVIg, SC Ig, or iv corticosteroids or the last PEX session, unless there is a medical reason, and an earlier treatment initiation is being considered █ for the study participant as agreed upon with the Medical Monitor and/or UCB Study physician.

The date and time of rescue medication administration as well as the name and dosage regimen of the rescue medication must be recorded.

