3.9 Changes to protocol-defined analyses

In the protocol section 9.2.1, the intercurrent events to be considered are the use of rescue therapy prior to Day 43 and permanent treatment discontinuation (or withdrawal from study) due to TEAEs. In the SAP, we consider use of rescue therapy prior to Day 43 and permanent treatment discontinuation due to TEAEs as intercurrent events.

In the protocol, the treatment policy strategy is described for the analysis meaning that all data was planned to be analyzed regardless of study participants receiving treatment with rescue therapy. Summaries will also be presented for the efficacy endpoints where participants will be censored at the time that they take rescue medication. In the SAP, time to MG-ADL response will be analyzed censoring the data at the time of the use of rescue therapy and all other efficacy endpoints will be summarized following treatment policy.

Protocol amendment 3 did not mention how to treat IgG when participants receive rescue therapy. In the SAP, the IgG values up to and including 8 weeks after start date of rescue therapy will be excluded from the analysis.

In the protocol section 8.3.1, Hy's law is defined as $>3 \times \text{ULN}$ ALT or AST with coexisting $>2 \times \text{ULN}$ total bilirubin in the absence of $<2 \times \text{ULN}$ ALP, with no alternative explanation for the biochemical abnormality (ie, without waiting for any additional etiologic investigations to have been concluded). In this SAP, Hy's law is defined as (AST or ALT $\geq 3 \times \text{ULN}$) and TBL $\geq 2 \times \text{ULN}$ and ALP $< 2 \times \text{ULN}$ to be consistent with Rozanolixizumab program SAP.

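### SAP 10.2.2 has no rescue-therapy rule for anti-AChR and anti-MuSK, although SAP 10.2.1 excludes total IgG and IgG subclasses for 8 weeks after rescue starts

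*SAP*

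**What the plan says.** **Total IgG and subclasses.** SAP 10.2.1 uses data before rescue starts and data from 8 weeks after that date. The values between, from the start date "to 8 weeks after start date of rescue therapy will be excluded from summary analysis", are left out and flagged in the listing. SAP 3.9 repeats the rule for IgG alone: "the IgG values up to and including 8 weeks after start date of rescue therapy will be excluded from the analysis".

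**Autoantibodies.** SAP 10.2.2 plans observed values, absolute and percentage changes, median plots and "The maximum change from Baseline in MG-specific autoantibodies". It contains no exclusion, censoring or flag at rescue. The endpoint in SAP 2.2.3.2 is the change "in MG-specific autoantibodies at each scheduled assessment during the Treatment and Observation Periods", so samples taken after rescue can fall inside it.

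**Protocol.** Section 9.4.2.2 puts both measures under one heading: "The PD endpoints will include serum total IgG, IgG subclass levels, and anti-MuSK and -AChR autoantibodies". Its rescue rule then covers only one of them: "For the analysis of the IgG data, in case rescue therapies are taken, only the data up to the start date of rescue therapy" is to be used.

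**Rescue.** Under Protocol 6.5.4, rescue means IVIg, SCIg, PEX or plasmapheresis, or iv corticosteroids. Rescue in the Treatment Period ends rozanolixizumab, with follow-up through the first 8 weeks of the Observation Period and then the EOS visit. Otherwise, "Those patients who received rescue therapy during the observation or no treatment with rozanolixizumab periods may continue in the study", subject to discussion with the sponsor's physicians.

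**The concern.** The protocol introduction itself links rescue-type procedures to the analyte summarised in SAP 10.2.2: "Treatments aimed at reducing the quantity of circulating IgG autoantibodies, including plasmapheresis, immunoabsorption, or high dose IVIg" are described there as established therapies for autoimmune disease. An autoantibody value measured soon after such a procedure may reflect the procedure, the study drug, or both. For total IgG the SAP has a rule for this situation. For the autoantibodies nothing is said, so the values stay in by default. The treatment-policy statement in SAP 3.9 does not fill the gap, because it is limited to efficacy endpoints.

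At stake is how the autoantibody pharmacodynamics are read. SAP 10.2.2 also plans a figure with the median percentage change in anti-MuSK (repeated for anti-AChR) beside that of total IgG. For a rescued participant, one curve would keep visits that the other drops.

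**Working it through.** The plan states no figure on this point. The check is a comparison of rules, some day arithmetic, and an illustration on assumed inputs.

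**1. Which samples fall in the 10.2.1 window (8 × 7 = 56 days from rescue start)?** Autoantibodies are sampled at about Days 1, 22, 43, 99 and EOS in the initial cycle, and at Days 1, 43 and EOS later. The later-cycle table is misaligned in the text as read. Day 43 is inferred because the autoantibody row matches the ADA row, which SAP 10.3.1 places at Day 43. A sample on Day d is inside the window if rescue started between Day d − 56 (or Day 2, if later) and Day d:
- Day 43: rescue started on Days 2 to 43, so in the Treatment Period.
- Day 99 (initial cycle): rescue started on Days 43 to 99.
- EOS after Treatment Period rescue: if EOS is 56 days after the last dose and rescue began on or after that dose, EOS is at most 56 days after rescue start.

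In each case 10.2.1 drops the IgG value, while 10.2.2 keeps the autoantibody value.

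**2. Direction within the rescue cycle.** If rescue lowers the autoantibody further, the recorded decrease is deeper. The maximum change can pick up that value if it lies below the on-treatment values.

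**3. Direction in the next cycle.** Protocol 6.5.4 sets a usual minimum of 4 × 7 = 28 days from the last rescue dose or session to the next cycle, and 28 < 56. That cycle's Day 1 can therefore fall inside the window. Its Day 43 sample comes 42 days later, at least 28 + 42 = 70 days after rescue, so it is outside. With true Baseline B and on-drug level P, the percentage change is 100 × (P/B − 1). If rescue lowers Baseline to rB with r < 1, it becomes 100 × (P/(rB) − 1), which shows a smaller decrease for the same P.

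**4. Size within a cycle (assumptions, not document figures).** Let f be the share of a cycle's participants rescued and e the extra fall in the lowest value, in percentage points. The shift in the mean maximum change is f × e:

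| f | e = 5 | e = 10 | e = 20 |
|---|---|---|---|
| 2% | 0.1 | 0.2 | 0.4 |
| 5% | 0.25 | 0.5 | 1.0 |
| 10% | 0.5 | 1.0 | 2.0 |
| 20% | 1.0 | 2.0 | 4.0 |

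A simulation (drug-only maximum change normal, mean −55%, SD 15) gave median shifts from 0.1 (f = 2%, e = 5) to 3.5 (f = 20%, e = 20).

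**5. Small groups.** One rescued participant among 5 is f = 1/5 = 20%, the last row: 1.0 to 4.0 points. Five is the minimum category size in SAP 4.9.1, used here only as an example of a small group.

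**The case against.** The other side has good points, and most of them limit the size and direction of the effect.

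- **The reason for the IgG exclusion is not stated.** A reader might infer that IgG is dropped because rescue lowers it, so that omitting autoantibodies contradicts the SAP's own logic. The documents do not say that. The amendment log speaks only of adding more valid data. A reason specific to total IgG is available: IVIg infuses IgG and so adds to the measured quantity. That would not carry over to anti-AChR or anti-MuSK. It also would not explain why the 10.2.1 rule covers PEX and iv corticosteroids, so the asymmetry still needs a stated decision.
- **Not every rescue therapy is covered.** The quoted introduction names neither SCIg nor iv corticosteroids as lowering autoantibodies.
- **Sampling is sparse.** A reader might infer that the maximum change will pick a low point after PEX and so overstate the drug effect. Most later cycles have one post-Baseline sample, and rescue can reach it only in participants who must then stop rozanolixizumab. Day 99 is 63 days after the last scheduled dose (99 − 36), so a rescue-lowered value there must fall below the on-treatment values to count.
- **A large effect is not supported.** Assuming an extra 30 to 50 points at 2% to 10% rescued would give 0.02 × 30 = 0.6 to 0.10 × 50 = 5 points. Those rates are undocumented. On an illustrative drug-only mean of −55%, another 50 points would be a fall of 105%, which is impossible.
- **The joint figure already mixes rules.** It also carries MG-ADL, QMG and MG-C mean changes, which follow treatment policy, and its antibody and IgG curves are medians. That weakens the plot argument but leaves the difference between the autoantibody and IgG curves.
- **A trace exists.** Autoantibodies are listed beside IgG, where excluded IgG values are flagged.

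**Conclusion.** The gap is real and minor. The SAP has a rescue rule for total IgG and subclasses and none for the autoantibodies, while the protocol describes plasmapheresis and high-dose IVIg as acting on IgG autoantibodies. Values taken after rescue could distort the by-visit, maximum-change and median summaries in a few participants, in either direction. The documents do not support saying that autoantibody reduction will be overstated.

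No rescue rate or rescue effect is given, so the size is unknown. On the assumed ranges above, the shift in the mean maximum change within a cycle is 0.1 to 4.0 percentage points, and 0.1 to 2.0 if no more than 10% are rescued. The next-cycle Baseline effect was not sized. This is a descriptive endpoint under the other objectives, so the point is a cheap improvement and threatens no main conclusion.

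**What to change.** - In SAP 10.2.2, apply the 10.2.1 exclusion to all autoantibody summaries and plots. Use the same 8-week window and the same anchor in both sections. The current anchor is the start of rescue. Counting from the last dose or session in one section only would recreate the mismatch.
- Flag the excluded autoantibody values in the listing, as is done for IgG.
- State, for IgG and autoantibodies alike, what happens when a cycle Baseline falls inside the window. If the value is treated as missing, the SAP 3.3 fallback would bring in one from a previous cycle or lead-in study. Say whether that is intended or whether change from Baseline is left uncalculated for that cycle.
- In the same edit, correct SAP 3.9. It says the amended protocol is silent on IgG after rescue, but Protocol 9.4.2.2 has a rule, and that rule stops at rescue start without re-admitting later data.

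The cost is a few sentences in the SAP and a few lost values, felt most in small groups such as anti-MuSK positives. If the sponsor prefers to keep all values, an all-data summary with a stated reason can stand beside the excluded one.
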